8.5 Analysis of Tertiary Outcomes

8.5.1. STI Risk

STI risk (gonorrhea; chlamydia) measured at 12 months (yes/no). We will use the same analysis techniques as proposed for the primary binary outcome (see Section 8.3.1). If there are few events and it is not possible to adjust for site, we will conduct a chi-square test of association.

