5. RANDOMIZATION

5.1 Method of Randomization

Randomization occurred on the participant level. Participants were randomly assigned to receive one of the following three conditions: ESTEEM, CMHT, or VCT-only (N = 250 across both sites). We used a 2:2:1 randomization scheme such that for every two participants randomized to ESTEEM, two participants were randomized to CMHT and one participant was randomized to VCT-only. Randomization happened through a computer-generated program stratified by site, such that 150 were randomized at the NYC site (60 ESTEEM, 60 CMHT, 30 VCT-only) and 100 were randomized at the Miami site (40 ESTEEM, 40 CMHT, 20 VCT-only). On 2/28/18, we discovered a programming error in the randomization and participants were not being randomized 2:2:1. The randomization was corrected to ensure the final distribution was 2:2:1 and the sample size was increased to 254 to accommodate.

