5.2 Allocation Concealment

An important consideration is allocation concealment to control for selection bias. Potential approaches include 1) randomizing after enrollment, 2) masking the recruiters, 3) standardizing the enrollment process with adequate training of screeners and recruiters, and 4) covariate adjustment in the analysis. We used approaches 1 through 3, and will employ approach 4, if necessary. Specifically, Qualtrics was initially used to randomize participants but was found to be doing so in error, using a 1:1:1 allocation, rather than the proposed 2:2:1. In February 2018, the following update was made: Team members agreed to a solution whereby the study changed the randomization scheme to correct for the previous 1:1:1 randomization and slow the rate of participant randomization to VCT. This was done through the use of a randomization strategy that would increase the probability of participants being assigned to ESTEEM and CMHT, and that by the end of the study would yield a 2:2:1 ratio. Based on the number of participants that were randomized from each site and their current allocation to treatment arms, it was determined that a 3:3:1 ratio of randomization should be used at each site to ensure the originally proposed balance of 2:2:1 be met by study's end. Further, it was recommended that participants be randomized in blocks at each site of 7 (3:3:1). This provision made sure that the each site retained the correction ratio consistently through the end of recruitment. At the time, to meet recruitment goals, 54 participants were remaining to be enrolled at the NYC site and 82 participants were remaining to be enrolled at the Miami site. As a precaution, the statistician recommended that each site complete a recruitment block of 7 regardless of targeted enrollment numbers. Using the remaining participants and the original target enrollment, it was suggested that NYC enroll *at least* 56 more participants (8*7) and Miami enroll *at least* an additional 84 participants (12*7). Using the SAS procedure 'Proc Plan,' 2 lists were generated per site using the block randomization method described. Based on the suggested allocation per site, a total of 140 participants were randomized to complete the study to provide a 2:2:1 balance. Envelopes containing the randomization codes were created numbered 1 to 140 per site. These envelopes were provided to each site with a tracking sheet (site list). Each envelope contained an assignment that matches each site list. When each participant was deemed eligible, the next envelope (in sequential order) was opened and treatment assigned. The

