8.2 Comparability of Treatment Groups

To determine randomization effectiveness, differences in baseline demographic characteristics will be assessed between ESTEEM, CMHT, and VCT-only groups using appropriate graphical and statistical methods including summary statistics. The randomization is designed to produce balance on important covariates. If we find imbalance on key covariates, we will consider sensitivity analyses that adjust for those covariates. Study site will be included as a covariate in all analyses because randomization was stratified by study site.

STATISTICAL ANALYSIS PLAN

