8.3 Analysis of Primary Outcome: HIV-Risk Behavior (Condomless Anal Sex)

8.3.1 Primary Analysis of Primary Outcome: Condomless Anal Sex

Analysis	Primary analysis of primary outcome: condomless anal sex in the absence of either PrEP or known undetectable viral load of HIV+ primary partners, measured with the TLFB, a semi-structured interview.
Analysis population	All enrolled participants
Endpoint	8-month as reported on TLFB
Unit of analysis	Participant
Method of analysis*	Generalized linear mixed model with a log (log-binomial) link using a contrast to test the comparison at the primary time point of 8 months adjusting for site and race/ethnicity (Wacholder 1986). We will conduct the comparison of ESTEEM versus VCT at 0.05 level; only if this test is statistically significant will we test ESTEEM versus CMHT at 0.05.
Handling of missing data	MAR assumption
Adjustment covariates	Study site (NYC or Miami).
Type I error	5% (2-sided)
Control of type I error	We will use a gatekeeping strategy. If the first comparison is significant at 0.05, then we will conduct the second comparison at 0.05.
Treatment effect estimate	Risk ratio with 95% confidence limits

*If the log-binomial approach fails to converge, we will use a modified log-Poisson model (Zou 2004).

Sensitivity analysis: This will only be conducted if baseline imbalance of covariates is found (see Section 7.2). Adjustment for baseline covariates not balanced at randomization.

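### The last-resort chi-square for STI risk drops the site stratum, relies on a large-sample test where events are sparsest, and names no effect estimate

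*SAP*

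**What the plan says.** SAP 4.3 lists a 12-month diagnosis of gonorrhoea or chlamydia as a tertiary outcome, and SAP 6.4 states that tertiary outcomes were not powered.

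For its analysis, SAP 8.5.1 says "We will use the same analysis techniques as proposed for the primary binary outcome (see Section 8.3.1"). Section 8.3.1 is a log-binomial mixed model with pairwise contrasts, ESTEEM versus VCT-only and then ESTEEM versus CMHT, at two-sided 5%. It moves to a modified Poisson model if the first fails to converge, and it reports "Risk ratio with 95% confidence limits".

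Section 8.5.1 then adds the last resort: "If there are few events and it is not possible to adjust for site, we will conduct a chi-square test of association".

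The general rule in SAP 8.2 is: "Study site will be included as a covariate in all analyses because randomization was stratified by study site". SAP 5.1 confirms the stratification: "Randomization happened through a computer-generated program stratified by site".

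SAP 5.2 reports that allocation first ran in error "using a 1:1:1 allocation, rather than the proposed 2:2:1", and then at 3:3:1 in blocks of seven at both sites. At the change, "54 participants were remaining to be enrolled at the NYC site and 82 participants were remaining to be enrolled at the Miami site".

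**The concern.** The last resort has three weaknesses.

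1. It leaves out site. That would matter little if every site had the same arm mix. Here the change from 1:1:1 to 3:3:1 came when New York was well advanced and Miami had barely started, so VCT-only should be a larger share of New York than of Miami. An unstratified comparison with VCT-only then absorbs part of any difference between the cities in STI prevalence.
2. It chooses a large-sample test for the situation in which expected counts are smallest. It does not say whether a continuity correction applies, whether the test is pairwise or across three arms, or how few events count as few.
3. It names no effect estimate or interval, whereas 8.3.1 specifies both.

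At stake is how the main infection outcome in SAP Table 1 would be reported if positives are rare: possibly a bare p-value, slightly shifted by site, with the version of the test open to choice after the data are seen.

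**Working it through.** **Inputs.** Site targets are 150 (New York) and 100 (Miami) (Protocol Section V, targeted enrolment; SAP 6.2). Remaining to enrol at the change: 54 and 82. Planned after the change: 56 and 84, total 140 (SAP 5.2). Final sample: 254 (SAP 6.2). The documents give no STI prevalence, so the prevalences below are assumptions.

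**Reproducing the stated total.** Before the change: 150 − 54 = 96 in New York and 100 − 82 = 18 in Miami. Then 96 + 18 + 140 = 254, which matches.

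**Expected arms by site** (first phase at 1:1:1, second at 3:3:1):

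| Site | ESTEEM | CMHT | VCT-only | VCT-only share |
|---|---|---|---|---|
| New York | 32 + 24 = 56 | 56 | 32 + 8 = 40 | 40/152 = 26.3% |
| Miami | 6 + 36 = 42 | 42 | 6 + 12 = 18 | 18/102 = 17.6% |
| Total | 98 | 98 | 58 | 58/254 = 22.8% |

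New York supplies 56/98 = 57.1% of ESTEEM but 40/58 = 69.0% of VCT-only, a gap of 11.8 percentage points. ESTEEM and CMHT have the same expected site mix.

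**Site bias in the crude comparison, no treatment effect.** With prevalence p in New York and q in Miami, the crude risk ratio is [(56p + 42q)/98] ÷ [(40p + 18q)/58].

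| Assumed p / q | ESTEEM | VCT-only | Crude ratio |
|---|---|---|---|
| 10% / 4% | 7.43% | 8.14% | 0.91 |
| 15% / 5% | 10.71% | 11.90% | 0.90 |
| 5% / 10% | 7.14% | 6.55% | 1.09 |

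A wider assumption, 5% / 15%, gives 9.29% ÷ 8.10% = 1.15. In absolute terms the bias is about 0.118 × (p − q), so a 10-point site difference shifts the risk difference by about 1.2 points.

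**Where the large-sample test becomes doubtful.** Expected VCT-only events fall below 5 when pooled prevalence is under 5/58 = 8.6%. With 80% retention (the SAP's 8-month figure, assumed to hold at 12 months) VCT-only has about 46 participants and the threshold is 5/46 = 10.9%.

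**Whether the choice of test matters.** Take 1/98 in ESTEEM and 4/58 in VCT-only. Here |ad − bc| = |1×54 − 97×4| = 334, N = 156, and the product of the margins is 98 × 58 × 5 × 151 = 4,291,420.

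- Uncorrected chi-square: 156 × 334² / 4,291,420 = 4.06, p = 0.044.
- Continuity-corrected: 156 × (334 − 78)² / 4,291,420 = 2.38, p = 0.12.
- Fisher exact, given 5 events: P(1 in ESTEEM) = 98 × C(58,4)/C(156,5) = 0.0576; P(0) = C(58,5)/C(156,5) = 0.0063. The opposite extreme, P(5) = 0.094, is more probable than the observed table and is not added. Two-sided p = 0.064.

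Most sparse tables do not cross 0.05 in this way: 0/98 versus 2/58 gives 0.064 (uncorrected) and 0.137 (Fisher), neither significant.

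**Whether site has to be dropped.** In simulations with no treatment effect, 80% retention, expected arm sizes and 400,000 replicates, a site-stratified Cochran-Mantel-Haenszel test ran without difficulty at 2% / 6% prevalence, with type I error 3.2% against 2.5% for the unstratified chi-square. Over all assumed prevalences from 2% to 20%, at full or 80% retention, the unstratified test ranged from 2.5% to 5.6%.

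**The case against.** The strongest reply is that this is a narrow contingency for an unpowered tertiary outcome, and that little harm follows. Much of that stands.

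- A reader might infer that site is dropped whenever events are few. The text does not say so. Events must be few **and** adjustment for site must be impossible, and 8.3.1, including modified Poisson, comes first.
- A reader might call 8.5.1 a contradiction of 8.2. It is better read as an explicit exception to a general rule. What survives is that failure of a regression model does not make stratification by a two-level factor impossible.
- A reader might say the STI result is confounded by city. That overstates it. At 15% / 5% the bias on the log scale is 0.105 against a standard error of √(1/10.5 − 1/98 + 1/6.9 − 1/58) = 0.46, about 0.23 standard errors. That scenario also implies about 28 events over three arms (152 × 0.15 + 102 × 0.05), where a site term could probably be fitted. At a sparser 3% / 1% (about 5.6 events) the ratio is again 0.90, but the absolute bias is 0.24 points and roughly 0.1 standard errors.
- A reader might expect an inflated false-positive rate. The simulations do not show a material one.
- The different arm mixes are expectations. SAP 5.1 and 5.2 describe the correction as achieving 2:2:1, and no counts by site and arm are reported.
- Section 8.5.1 does not say that the test is run across three arms, nor that the risk ratio is withdrawn. It is silent on both.

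The reply does not supply a reason to prefer an unstratified large-sample test in sparse data, or to leave the estimate unnamed.

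**Conclusion.** The point holds as a minor improvement. If the 8.3.1 model cannot adjust for site because STI events are few, the stated substitute leaves out the stratification factor, depends on large-sample theory where VCT-only expected events are likely to be under 5, and specifies no estimate or interval.

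The site bias is small, applies only to comparisons with VCT-only, and rests on two assumptions: that the realised arms are close to the expected counts, and that STI prevalence differs between the cities as assumed. The choice of test can decide nominal significance in some sparse tables but not in most. Nothing here touches the primary or secondary outcomes.

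**What to change.** Replace the last sentence of SAP 8.5.1 with:

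> If the 8.3.1 model, including the modified Poisson fallback, cannot be fitted because events are few, each pairwise contrast (ESTEEM vs VCT-only, then ESTEEM vs CMHT) will use an exact conditional test stratified by site, with a site-stratified Mantel-Haenszel risk ratio and 95% confidence limits; if an arm has zero events, a site-stratified risk difference or an exact conditional odds ratio interval will be reported instead.

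The final clause is needed because the usual Mantel-Haenszel limits are computed on the log scale and cannot be formed when an arm has no events. Before analysis, the authors should also settle which of its two options applies.

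The cost is one sentence, with no new data and standard procedures. The downside is that the exact test is somewhat conservative. Stratifying by site restores consistency with 8.2 but does not capture the change in allocation within each site, where the chance of VCT-only fell from 1/3 to 1/7.

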8.5.2 Mental health mediators

We will follow a similar analysis plan as proposed in 8.4.3 and 8.4.4 using the mental health variables as the mediators and determining the mediating relationship on HIV risk outcomes using both latent variable mediation models and mediation analysis with multiple mediators.

